9.2. Cannabis/THC Use

Patients utilizing cannabis/THC are to be excluded if MINI 7.0.2 criteria are met for greater than MILD Cannabis Use Disorder during the preceding 12 months (prior to the Screening visit), OR if the investigator is concerned that the patient's use of cannabis/THC could interfere with patient's ability to provide reliable data or comply with the protocol. Cannabis/THC use is otherwise allowed, with caution. The screening drug screen will also test for THC to provide the investigator with information regarding exposure, and to ensure that all usage is disclosed and taken into consideration when conducting MINI Module J.

9.3. Enrollment of Patients

Before undergoing any study-related screening procedures, each potential patient must provide written informed consent. The Investigator will then determine the potential patient's suitability for the study by interviewing the patient and by performing per-protocol screening assessments. If study drugs are to be withdrawn for the explicit purpose of participation in this study, the patient must have already provided consent and signed an informed consent form before the withdrawal or down titration of any drug is initiated.

10. STUDY DRUG MATERIALS AND MANAGEMENT

10.1. Study Drug Packaging, Labeling, and Storage

Study drug supplies will be packaged identically so as to maintain the integrity of the study blind. The study drug bottles will be labeled minimally with the following information: study number TNX-CY-F304, sponsor name and address, bottle number, quantity, storage conditions, usage instructions, and caution statements for investigational new drug, i.e., Caution: New Drug – Limited by United States Law to Investigational Use, and Keep Out of Reach of Children and Pets.

Each study drug bottle will contain 40 tablets. One bottle will be dispensed to each patient at Visit 2 (Baseline) and then two bottles will be dispensed at Visit 3 (Week 2), Visit 4 (Week 6), and Visit 5 (Week 10). Study drug will be mailed via courier to a patient's home where a telephone visit is scheduled to be conducted. This will provide the patient with enough tablets to cover the 2 or 4 weeks of dosing between visits, plus additional tablets to cover loss and/or visit window variability. The patient should be instructed to take all the tablets in one bottle before opening the second bottle. The patient should be instructed to keep this study drug in a safe location out of extreme environmental conditions and out of the reach of children and pets, and be instructed that this drug is not to be taken by any individual other than the study patient. Each patient will also be instructed that they are expected to return both bottles (even if empty) and all unused study drug at each clinic visit¹; unused drug will be counted to assess compliance with study drug treatment.

Storage of the study drug at the investigational site should be under locked and secure conditions with limited staff access. Study drug should be stored at 20-25°C/68-77°F in a temperature/humidity-monitored room; however, brief excursions (15-30°C/59-86°F) as defined in the Study Reference Manual (Investigational Product Receipt and Storage) are permitted without the sponsor's approval.

10.2. Dosing Instructions

Patients will be instructed to take 1 tablet of randomly assigned study drug TNX-102 SL 2.8 mg or SL placebo tablet sublingually, under the tongue, each evening at bedtime starting at bedtime on Day 1 (Day of Visit 2) and continuing through Day 14. At the Week 2 visit, patients will be instructed to increase the dose to 2 tablets at bedtime, administered simultaneously and under the tongue beginning on Day 15 and continuing through the end of the study.

The study drug should be taken at bedtime after teeth brushing and other oral care has been completed. The mouth/sublingual area should be moist at the time of dosing, so the patient should drink a few sips of water prior to dosing, especially if prone to dry mouth. Patients will be instructed to place the one or two SL tablets under their tongue (if two, placed simultaneously under tongue) and keep them there until they have dissolved (approximately 90 seconds). They should not swallow, crush or chew the tablets. Patients should not eat or drink (or chew gum) for at least 15 minutes after dosing, and preferably not to drink any hot, cold or acidic beverage until

¹ All references to a site/study center visit for Weeks 2, 6, 10, and 14 include telephone visits for Weeks 2, 6, and 10, and home visits or telephone visit for Week 14/ET that are being allowed due to the circumstances of the COVID-19 pandemic.

morning. Patients also should not talk for at least 5 minutes after placing the study drug in the mouth (under the tongue). Patients will be reminded that only 2 (two) tablets are allowed per day. Note: In the event that the patient misses a dose, instruct the patient to continue dosing with two (2) tablets the next evening; i.e., they should not take more to make up for the missed dose.

If the patient reports intolerable side effects that are likely to result in premature discontinuation from the study, then the dose of study drug may be reduced to one tablet sublingually nightly. Any reduction in study drug dose must be carefully documented in the CRF. The goal is for the patient to be on a stable and final dose of study drug starting from the Week 2 visit, at the highest dose tolerated (preferably two TNX-102 SL tablets daily at bedtime).

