visit in order to collect greater safety data than the telephone visits allow. The Screening phase will be followed by the Baseline/Randomization Visit (Visit 2, Day 1), and 4 treatment visits at Weeks 2, 6, 10, and 14 (or Early Termination). The total duration of the study, including Screening, will be approximately 15-19 weeks. The maximum treatment duration will be 14 weeks.

Eligible patients who provide written informed consent will have study assessments performed at Screening and will stop all excluded medications during the washout period through the Week 14 visit (Visit 6). Patients will record their average pain intensity for the previous 24 hours in the evening every day from Visit 1 through Visit 6 on a diary system. After recording Baseline Diary scores for at least 7 days, patients will return to the investigative site for Baseline assessments and randomization (Day 1), where they will be randomly assigned to receive TNX-102 SL or matching placebo sublingual tablets in a 1:1 ratio.

Patients will take the study drug sublingually daily at bedtime, starting on the day that they are randomized (Day 1), for 14 weeks. For the first two weeks of treatment, patients will start on TNX-102 SL 2.8 mg (1 tablet) or placebo. Upon return to the site¹ for the Week 2 visit (Visit 3), all patients will have the dose increased to TNX-102 SL 5.6 mg (2 x 2.8 mg tablets) or two placebo tablets. Patients will return to the site¹ for assessment of efficacy and safety, as well as dose tolerability, at Weeks 6, 10, and 14 (or Early Termination).

In scenarios in which TNX-102 SL 5.6 mg, or 2 placebo tablets, is considered intolerable and would otherwise lead to study discontinuation, the Investigator may lower the dose back to 1 tablet every night (TNX-102 SL 2.8 mg or one placebo tablet). Re-challenge with 2 tablets TNX-102 SL 2.8 mg (5.6 mg dose)/placebo may be attempted at a later date if/when it is deemed clinically warranted by the Investigator, or the patient may remain on the lower dose for the remainder of the study.

Patients who wish to withdraw from the study may do so at any time.

Patients will be trained on use of the diary system at the Screening visit. Each evening, when the patient utilizes the diary, the system will prompt the patient regarding daily average pain intensity, sleep quality from the previous night, and study drug dosing the previous night (post-randomization).

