Patients will take the study drug sublingually daily at bedtime, starting in the evening of the day that they are randomized (Day 1, Visit 2), for 14 weeks. Patients will be instructed to take one tablet (2.8 mg) sublingually daily at bedtime for the first 2 weeks (Days 1-14). Patients will then return to the clinic¹ at Week 2 (Visit 3) for efficacy and safety assessments, assessment of study drug compliance, and the study drug dose will be increased to two tablets (2 x 2.8 mg) taken sublingually and simultaneously daily at bedtime. Patients will next return to the clinic¹ at Week 6 (Visit 4) for efficacy and safety assessments, assessment of study drug compliance, and an assessment of dose tolerability at the 5.6 mg dose. If the patient reports intolerable side effects at this visit (Visit 4), the Investigator may consider a reduction in dose to one tablet sublingually every night, either temporarily or for the remainder of the study, depending on what the Investigator considers clinically appropriate. It will be emphasized to Investigators that such dosage reduction should only be considered when the patient's intolerability is sufficient to cause the patient to consider discontinuing from the study. It will be emphasized to participating patients that they should only make changes in study drug dose upon consultation with the Investigator, and they should notify the clinic immediately if they think the dosage needs to be adjusted. Ideally, any changes in dose should only be made at a scheduled visit, but, if necessary to change dose between visits, the change should only be made upon the recommendation of the Investigator after discussion between the patient and the Investigator. Patients will return to the study center¹ for safety and efficacy assessments, and assessments of study drug compliance and tolerability at Weeks 10 (Visit 5), and 14 (Visit 6) or Early Termination.

Patients who wish to withdraw from the study may do so at any time.

The study timeline and events schedule is provided in [Table 2](#).

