10.3. Dispensing Instructions

Each patient who has met the randomization criteria (Section 8.4) will be assigned a double-blind treatment bottle at Visit 2 via the Interactive Response Technology (IRT), with a unique, but otherwise random bottle number that is generated when the study coordinator successfully completes randomization procedures. Patients will take one sublingual tablet each evening before bedtime for the first 2 weeks.

Study treatments for the double-blind treatment phase are either:

Treatment A: 2 × TNX-102 SL 2.8 mg tablets (“TNX-102 SL”) to be taken sublingually (simultaneously) once daily at bedtime.

Treatment B: 2 × placebo tablet (“placebo”) to be taken sublingually (simultaneously) once daily at bedtime.

Beginning with the evening of the Week 2 Visit, patients will take 2 sublingual tablets each evening before bedtime, and will continue doing so throughout the course of the study. Only in the event of adverse events that might possibly lead to discontinuation can the patient reduce the dose to 1 tablet per evening, with approval of the Principal Investigator.

In the event of loss of a study drug bottle, a new bottle will be provided by the IRT when appropriately requested by the site and/or the sponsor or designee.

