11.2.2. Baseline Visit

For patients who have qualified for randomization, these assessments and procedures will be completed in the following general order:

- Confirm patient's eligibility based on the diary data collected during the preceding 7 days
- Review completed diary data with the patient
- Update medical history (with any changes noted since screening)
- Assess changes in medication history and concomitant medications
- Have the patient complete the BDI-II. If the BDI score is >24 , the patient is not eligible for randomization and should be screen failed. In addition, a score > 1 on item #9 (suicidal ideation) is exclusionary.
- Administer the "Since Last Visit" version of the C-SSRS. Any patient exhibiting Type 3, 4, or 5 suicidal ideation or any suicidal behavior since the Screening visit should be screen-failed and assessed for appropriate follow-up care.
 - a. Results of the C-SSRS and BDI-II should be reviewed together to ensure (1) the patient is not experiencing suicidal ideation or worsening depression that requires intervention and (2) both scales are providing a consistent clinical picture of the patient with regard to suicidality.
- Assess occurrence of adverse events
- Conduct a brief physical examination, including vital signs and weight
- Conduct a visual examination of the oral cavity. This examination should include a careful visual examination of the sublingual area, tongue, buccal mucosa, lips, palate and gums. Any abnormalities should be noted on the oral exam source document. It is recommended that both non-significant as well as significant findings be noted so that there is a complete and accurate baseline assessment available for comparison to findings at later visits.
- Perform urine pregnancy test (for women of child-bearing potential)
- Patient should complete the following patient-reported outcomes (PRO):
 - a. FIQR
 - b. Clinic administered assessment of pain by both 24-hour and weekly recall using 11-point (0-10) NRS scale
 - c. PROMIS scales for sleep disturbance and fatigue
 - d. CSFQ-14 female or male version, as appropriate
- Ensure that all PROs were accurately and fully completed

- Once it has been confirmed that the patient remains eligible, randomize patient via IRT Randomization System
- Dispense bottle of double-blind study drug as assigned via the IRT
- Review patient instructions regarding study drug dosing and diary completion (Section 10.2 and Section 12.2.6).

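### The only missed-dose rule (Protocol 10.2) is worded for two-tablet patients but does not say so; applied literally to a one-tablet patient on active drug it gives 5.6 mg instead of 2.8 mg for one night

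*Protocol*

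**What the plan says.** Protocol Section 10.2 starts every patient on one tablet at bedtime through Day 14 and then moves to two from Day 15. Section 10.3 agrees: "Patients will take one sublingual tablet each evening before bedtime for the first 2 weeks". For a patient who cannot tolerate two tablets, Section 10.2 adds: "then the dose of study drug may be reduced to one tablet sublingually nightly". Under Section 7.1 that reduction may be temporary or may last to the end of the trial.

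The administration paragraph of Section 10.2 covers both dose levels: "Patients will be instructed to place the one or two SL tablets under their tongue". Its last two sentences are a daily limit, "Patients will be reminded that only 2 (two) tablets are allowed per day", and the missed-dose note, which has staff give this direction: "continue dosing with two (2) tablets the next evening; i.e., they should not take more to make up for the missed dose".

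Two other provisions bear on the point. A return to two tablets after a reduction "may be attempted at a later date if/when it is deemed clinically warranted by the Investigator" (Synopsis). Patients are also told that "they should only make changes in study drug dose upon consultation with the Investigator" (Section 7.1).

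**The concern.** The note names a number of tablets, not the patient's assigned dose, and sets no condition on study day or current dose. It is written for staff to pass on. At Visit 2, when every patient is about to start on one tablet, Section 11.2.2 sends staff to Section 10.2 for the dosing instructions. A one-tablet patient who misses a night therefore has either no rule or, if the note is taken at its word, a rule that doubles the next dose.

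For a titrating patient, that would bring the target dose forward by some days, for one night. For a reduced patient, it would be a night back on the dose found intolerable, without the Investigator's judgment that re-challenge requires.

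**Working it through.** **Is there another missed-dose rule?** None was found in the Synopsis, in Protocol Sections 7.1, 10.3, 11.2.4, 11.3 and 11.4, or in the SAP. Protocol 12.2.6 deals with missed diary entries. SAP 12.3 counts days without a diary entry as days without drug, which is a rule for exposure summaries and not for dosing.

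**Dose.** The tablet strength is 2.8 mg.
- Two tablets: 2 × 2.8 = 5.6 mg, which reproduces the protocol's stated full dose.
- One tablet: 1 × 2.8 = 2.8 mg.
- Note applied to a one-tablet patient on active drug: 5.6 mg against 2.8 mg assigned, an excess of 2.8 mg that night (a factor of 2). On placebo it is one extra placebo tablet.

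**Would the daily limit or the supply prevent it?** The limit is two tablets for everyone, so it does not bind. The Visit 2 bottle holds 40 tablets (Protocol 10.1), of which 14 are scheduled through Day 14, leaving 40 − 14 = 26.

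**Would the tablet count in Protocol 10.5 show it?** Take a one-tablet patient who misses k nights in a row and then takes two tablets. Scheduled: k + 1. Taken: 2. Shortfall: (k + 1) − 2 = k − 1.

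| Misses in a row | Scheduled | Taken under the note | Shortfall | Shortfall if one tablet is resumed |
|---|---|---|---|---|
| 1 | 2 | 2 | 0 | 1 |
| 2 | 3 | 2 | 1 | 2 |

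After an isolated miss the count balances, so the count alone would not reveal either the miss or the double dose. The diary can: it asks whether drug was taken the previous night and, if so, whether it was one tablet or two (Protocol 12.2.6).

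**On which titration nights could it arise?** On the Section 10.2 schedule there are 14 one-tablet nights. A miss on Day 14 is followed by a night when two tablets are due anyway, which leaves Days 1–13, or 13 nights. Section 10.3 starts two tablets on the evening of the Week 2 visit, and that visit may fall from Day 11 to Day 22 (Day 15 −4/+7). One-tablet nights then number 10 to 21, and the eligible ones 9 to 20. These are counts of nights on which the situation could arise, not estimates of how often it would.

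**Would it reach the primary analysis?** The model in SAP 10.1.2 uses randomized treatment, site, week and baseline, with no term for tablets taken. The summaries by dose in SAP 10.4 group patients by Investigator-directed reduction and not by the dose taken at a given time.

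**The case against.** The strongest reply is that the note limits itself. A patient on one tablet cannot continue with two, and the clause after the semicolon forbids the extra tablet in question. The note also follows the description of the Week 2 increase. Section 10.3 likewise labels both treatments as two tablets although the first two weeks use one, so two tablets looks like the protocol's shorthand for the standard regimen. This stands as a reading of intent. It does not supply a written scope, and it leaves one-tablet patients without a missed-dose rule of their own.

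A second reply is that other provisions protect these patients. The one-tablet schedule is stated clearly in several places, dose changes go through the Investigator, the diary records tablets per night, and Section 10.5 requires staff to check that dosing instructions are understood. These do limit the risk. The consultation rule, however, mainly restrains patients acting alone, whereas here staff would be giving the instruction from the protocol. The diary finds the event only afterwards.

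A third reply is that 5.6 mg is the planned dose from Day 15. That is right for titrating patients and is why the consequence for them is slight. It does not answer for a patient whose dose was reduced because two tablets were intolerable.

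A reader might go further and infer that the protocol prescribes a double dose for one-tablet patients, or that the titration design is unsafe. The documents support neither. The wording points to patients already on two tablets, the stated aim is to prevent make-up dosing, and any harm depends on staff applying the note outside that evident purpose.

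**Conclusion.** The point holds as a minor error in a dosing instruction: the rule's scope is implied but not written, and a literal application to a one-tablet patient contradicts the rule's own ban on make-up dosing. The size is one night at 5.6 mg instead of 2.8 mg, in the active arm, for each isolated miss or run of misses to which the note is misapplied. This takes the next evening to mean a single night.

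Safety relevance is small. It rests mainly with patients reduced for intolerance, and Protocol 5.4 expects reductions to be rare. The conclusion is conditional on staff following the note literally. Neither document gives a rate of missed doses or reductions, so no number of affected patients is estimated. The bottle usage instructions and the Study Reference Manual, which may word the rule correctly, are not among the documents. Confidence is therefore high about the wording and limited about any practical effect.

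**What to change.** Replace the missed-dose note in Protocol 10.2 with: *resume the currently assigned dose (one or two tablets) the next evening; do not take extra tablets to make up for the missed dose*. In the sentence before it, give the daily maximum as the currently assigned number of tablets. Check that the bottle label and the Study Reference Manual say the same.

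The cost is a short protocol clarification. No data collection or analysis changes.

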10.3. Dispensing Instructions

Each patient who has met the randomization criteria (Section 8.4) will be assigned a double-blind treatment bottle at Visit 2 via the Interactive Response Technology (IRT), with a unique, but otherwise random bottle number that is generated when the study coordinator successfully completes randomization procedures. Patients will take one sublingual tablet each evening before bedtime for the first 2 weeks.

Study treatments for the double-blind treatment phase are either:

Treatment A: 2 × TNX-102 SL 2.8 mg tablets (“TNX-102 SL”) to be taken sublingually (simultaneously) once daily at bedtime.

Treatment B: 2 × placebo tablet (“placebo”) to be taken sublingually (simultaneously) once daily at bedtime.

Beginning with the evening of the Week 2 Visit, patients will take 2 sublingual tablets each evening before bedtime, and will continue doing so throughout the course of the study. Only in the event of adverse events that might possibly lead to discontinuation can the patient reduce the dose to 1 tablet per evening, with approval of the Principal Investigator.

In the event of loss of a study drug bottle, a new bottle will be provided by the IRT when appropriately requested by the site and/or the sponsor or designee.

10.4. Release of Clinical Study Supplies to the Investigator

Tonix or Tonix’s designee’s standard operating procedures for releasing clinical trial supplies to the site will be followed.

10.5. Study Drug Accountability and Reconciliation

All patients will be expected to bring their bottles of study drug with them to all study visits (including empty bottles), unless a telephone visit, where patients will be asked to count the number of tablets remaining in their current bottles, document this on a form provided to patient, and return this form and study drug (with bottles) via courier to the site. At each study visit, the site staff will inspect the drug bottles, and perform a count of the tablets remaining in the bottles and document this in the patient's record. For telephone visits, drug accountability by the site staff will occur after the study drug is returned to the site via courier. For home visits (Week 14 or ET only), site staff will collect bottles and conduct accountability upon return to the site. An assessment of drug adherence should be done by the study staff to ensure that the patient understands all dosing instructions and is taking the drug as prescribed. Patients will be asked for an explanation if the count of returned study drug tablets indicates a discrepancy between the expected number of tablets dosed and the number returned in the bottles. If it is found that the patient is not taking the study drug as expected, the patient will be re-counseled with instructions, and this should be noted in the patients' records. A deviation should be recorded on any patient who is less than 70% compliant with dosing between visits and one of the Medical Monitors should be contacted.

Tonix or its designee will perform drug accountability which entails reconciliation between the amount of drug shipped to the study site, study drug assigned and dispensed to the patient (including returned unused assigned study drug), and study supplies that were never dispensed and/or assigned to patients.

